7.2. Participant Disposition

Participant disposition analyses will use the SS unless otherwise stated.

The following disposition categories will be summarized:

- Number (%) of participants who received at least one dose of study treatment
- Number (%) of participants who are still on treatment
- Number (%) of participants who discontinued the treatment
- Primary reasons for treatment discontinuation
- Number (%) of participants who discontinued the treatment but are still in follow-up for disease or for survival
- Number (%) of participants who discontinued the study
- Primary reasons for study discontinuation

Inclusion and exclusion criteria for each of the analysis sets will also be summarized.

Participant disposition data will also be listed.

Screen failure participants are those who were screened, but never started the study treatment for any reason. The data collected on these participants will not be included in any analyses. A listing of reasons for screen failure will be presented.

A separate listing will describe each participant's inclusion or exclusion status for each of the analysis sets defined in [Section 5](#).

7.3. Protocol Deviations

Protocol deviations will be determined and documented prior to database lock as outlined in the *Specifications of Protocol Deviations*. Categories and significance of protocol deviations will be assigned according to the deviation rules document. The number and percentage of participants in the SS with any significant protocol deviations will be tabulated by the deviation category.

Significant protocol deviations will be presented in a data listing by participant. In addition, protocol deviations due to COVID-19 will be presented in a separate table and listing.

7.4. Participant Characteristics

Participant characteristic analyses will be performed using the SS.

7.4.1. Demographics and Pretreatment Characteristics

Demographic and other pretreatment characteristics including age, gender, race, ethnicity, height, weight, and ECOG performance status at baseline will be summarized.

In addition, the tobacco use status collected on the Tobacco Use eCRF page will be summarized (current smoker, former smoker, and non-smoker), considering cigarette, cigar, pipe, e-cigarette, and vape.

A demographics listing by participant will be presented.

7.4.2. Medical and Disease History

Medical history reported at screening will be coded using the latest MedDRA terminology available at the time of reporting. Medical history will be summarized by primary SOC and PT for ongoing and past disease. Each participant will be counted only once within each PT and SOC.

The summary of disease history will include time since initial diagnosis (months), TNM (AJCC staging) at diagnosis, TNM (AJCC staging) at study entry, tumor histology, and presence of brain metastases.

7.4.3. BRAF Status

BRAF status will be summarized based on the data collected in the “BRAF Status” eCRF page for local testing results and data from the central laboratory for central testing results, if data available. The following information will be included in the summary: BRAF status (including tissue sample status [fresh or archive], site [primary or metastatic], irradiation status of site, method of testing, and testing results).

Concordance between BRAF status from local and central laboratory at screening will be summarized, if data from central laboratory will be available. Additional analyses and details will be included in a statistical analysis plan for companion diagnostic development.

BRAF status data for local test will also be listed for each participant.

7.4.4. Prior Anticancer Therapy

Prior anticancer therapy will be summarized for three distinct subtypes (systemic treatment, radiotherapy, and surgery). The number (%) of participants who received, separately, any prior systemic treatment, radiotherapy, or surgery will be summarized.

For prior systemic treatment, the following data will be summarized including for all setting and for drugs received for metastatic disease only:

- Number and percentage of participants with at least one prior systemic treatment
 - Number of participants who received prior immune therapy (monotherapy or combination therapy)
 - Number of participants who received monotherapy PD1/L1
 - Number of participants who received combination PD1/L1 therapy (with chemotherapy or other immune therapies)
 - Number of participants received chemotherapy without immune therapy
- Total number of regimens (there can be more than one medication per regimen) and total number of regimens for metastatic disease.
- Setting (adjuvant, neoadjuvant, locally advanced, metastatic) at last medication
- Best response by type of therapy (monotherapy PD1/L1, combination PD1/L1 therapy, chemotherapy without immune therapy) at last medication (defined as the best response during the last treatment regimen recorded)
- Time (in months) from start of last regimen for metastatic disease to disease progression. The last regimen is defined based on the last number of all prior regimens with a setting equal to metastatic, locally advanced, maintenance, palliative.

Prior systemic treatments for metastatic disease will also be summarized by ATC class and PT.

For prior anticancer radiotherapy, the following information about the last radiotherapy (based on end date) will be summarized: time (in months) between radiotherapy and start of study treatment, location, best response, radiation therapy type, setting (adjuvant, neoadjuvant, palliative, metastatic), and whether radiation was given with chemotherapy.

For prior anticancer surgery, the time (months) between last surgery and start of study treatment, site, location, whether the surgery was palliative, and the result will be summarized.

All prior anticancer therapies will be listed separately for systemic treatment, radiotherapy, and surgery.

Incomplete dates will be handled as described in [Section 7.1.11](#).

7.4.5. Other Prior Medications

Prior medications are any medications (excluding study drug and prior anticancer treatments) which started before first dose of study drug. Prior medications will be summarized based on the Prior and Concomitant Medications eCRF. These medications will be coded using the WHO DRL dictionary that employs the WHO ATC classification system.

The number and percentage of participants with prior medications will be summarized by ATC classification level 2 and preferred term (level 4).

Incomplete dates will be handled as described in [Section 7.1.11](#).

7.5. Efficacy Analysis

SS will be the primary population for the analysis of all efficacy endpoints. Depending on the recruitment rate for previously treated participants, a primary analysis may be performed separately for the treatment-naïve participant population. In any case, data will be summarized for treatment-naïve participants, previously treated participants, and overall.

The final analysis for ORR (Primary Completion Date) for treatment-naïve participants will take place after 14 months from the enrollment of the last treatment-naïve participant.

All efficacy endpoints, except OS, will be evaluated by IRR and by derived investigator-assessment in participants with *BRAF*^{V600E} mutant NSCLC, as determined by local test. Endpoints for derived investigator (hereafter referred to as investigator) will be derived programmatically from the target lesion measurements, non-target lesion status, and new lesions recorded on the eCRF, see details in [Section 10 \(Appendix 1\)](#).

7.5.1. Objective Response Rate

Objective Response (OR) based on IRR is the primary endpoint and is defined as CR or PR according to RECIST version 1.1 from date of first dose of study treatment until documented PD or start of new anticancer therapy. Both CR and PR must be confirmed by repeat assessments performed no less than 4 weeks after the criteria for response are first met.

Clinical deterioration or clinical progression noted on the End of Treatment Disposition eCRF will not be considered as documented disease progression for the purposes of the ORR calculation.

The confirmed BOR for each participant is determined from the sequence of overall time point (lesion responses) according to the following rules below:

- CR = at least 2 determinations of CR at least 4 weeks apart before progression.
- PR = at least 2 determinations of PR or better at least 4 weeks apart before progression (and not qualifying for a CR).
- SD = an assessment of SD or better ≥ 6 weeks after start of treatment (and not qualifying for PD, PR or CR).
- PD = progression ≤ 16 weeks after start of treatment (and not qualifying for CR, PR, or SD).
- NE (Not Evaluable) = all other cases (i.e. not qualifying for confirmed CR or PR and without SD after more than 6 weeks or early progression within the first 16 weeks).

Participants with a BOR of 'Not Evaluable' will be summarized by reason for having unknown status. The following reasons will be used:

- No adequate baseline assessment
- No evidence of disease at baseline
- No post-baseline assessments due to early death (defined as death prior to 6 weeks after date of first dose)
- No post-baseline assessment due to other reason
- All post-baseline assessments have overall response of "NE"
- New anticancer therapy started before first post-baseline assessment
- SD occurred < 6 weeks after the start of treatment and no subsequent tumor assessments

- Progression >16 weeks after the start of treatment (i.e., tumor assessment of PD was >16 weeks after start of treatment and there was no tumor assessment in between).

Special (and rare) cases where BOR is ‘Not evaluable’ due to both SD occurring < 6 weeks after start of treatment and progression > 16 weeks after the start of treatment will be classified as “SD occurred < 6 weeks after the start of treatment”.

The ORR will be calculated with the exact 2-sided Clopper-Pearson 95% CI.

A sensitivity analysis will be performed for ORR by IRR in RE set at the time of interim analysis.

An additional analysis of ORR by IRR will be performed if participants with *BRAF*^{V600} mutant NSCLC other than V600E will be treated.

The impact of tumor assessments missing due to COVID19 will be evaluated and, if needed, a sensitivity analysis of ORR by IRR may be performed excluding participants with tumor assessments missing due to COVID19 from SS.

ORR by investigator assessment will be calculated with the exact 2-sided Clopper-Pearson 95% CI.

For ORR by IRR and investigator assessment additional subgroup analyses may be performed to explore the influence of various baseline characteristics [age group (<65 years and ≥65 years), gender, race group (Asian and non-Asian), and ECOG performance status (0 and 1)].

The total event disagreement rate for IRR and investigator responses will be presented.

Table 3. Definition of Agreement Used to Determine Total Event Agreement and Disagreement Rates in Response

	Investigator	IRR	Variable Name
Agreement	No response	No response	a
	Response	Response	b
Disagreement	No response	Response	c
	Response	No response	d

$$N = (a + b + c + d)$$

The total event disagreement rate measures the proportion of participants for whom there is a discrepancy between the IRR and investigator as to whether the participant was a responder

with either the IRR or the investigator, but not both, among all participants who are evaluated by both IRR and investigator.

$$\text{Total Event Disagreement Rate} = [(c+d) / N] \times 100\%.$$

The total event agreement rate measures the proportion of participants for whom there is a concordance between the IRR and investigator as to whether the participant was a responder or a non-responder with both the IRR and the investigator, among all participants who are evaluated by both IRR and investigator.

$$\text{Total Event Agreement Rate} = [(a+b) / N] \times 100\%.$$

A swimmer figure for duration of exposure and best overall response (confirmed) by IRR will be created.

A waterfall plot based on investigator will be created to show the best percentage change in target lesions from the baseline in the sum of longest diameters. Participants with baseline and at least one post-baseline tumor assessment will be included in the waterfall plot. The best percentage change in target lesions from baseline will be derived across all the post-baseline assessments until documented disease progression, excluding assessments after start of subsequent anticancer therapy, as follows:

$$\text{Minimum of } ((\text{sum of target lesions at week XX} - \text{sum of target lesions at baseline}) / \text{sum of target lesions at baseline}) * 100$$

Individual lesion measurements and overall response assessments per RECIST v1.1 will be listed by participant and assessment date by IRR and investigator.

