7.1.6. Adequate Postbaseline Tumor Assessment

An adequate assessment is defined as an assessment where a response of CR, PR, Stable Disease (SD), non-CR/non-PD (to be used if only non-measurable disease is present), or PD has been provided by IRR or the investigator for the analyses by IRR or investigator, respectively. Time points where the response is not evaluable or no assessment was performed will not be used for determining the censoring date for time to event endpoints.

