7.5.4. Disease Control Rate

DCR is defined as the proportion of participants who have achieved a confirmed CR, confirmed PR or SD, as determined by IRR and investigator per RECIST v1.1 after 24 weeks (≥ 168 days) from the date of first dose of study drug.

DCR will be calculated along with the exact two-sided Clopper-Pearson 95% CI.

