7.5.5. Progression-free Survival

Progression-free survival is defined as the time from the date of first dose of study drug to the earliest date of disease progression, as determined by IRR and investigator per RECIST v1.1, or death due to any cause, whichever occurs first, and will be summarized in months:

$$\text{PFS (months)} = [(\text{date of event or censoring} - \text{date of first dose}) + 1] / 30.4375.$$

Participants without an event or with an event more than 16 weeks (for the first 12 months after treatment start date) or 24 weeks (after the first 12 months of treatment start date) after the last adequate tumor assessment will be censored on the date of the last adequate tumor assessment that documented no progression. In addition, if a new anticancer therapy is started prior to an event, the participant will be censored on the date of the last adequate tumor assessment that documented no progression prior to the start of the new anticancer therapy. Note: if date of progression occurs on the same date as the start of new anticancer therapy, the progression will be counted as an event.

An adequate post-baseline assessment is defined as an assessment where a response of CR, PR, SD, non-CR/non-PD, or PD can be determined. Time points where the response is NE or no assessment was performed will not be used for determining the censoring date.

Participants with no baseline tumor assessment (including participants with an inadequate baseline assessment) or with no adequate post-baseline tumor assessments within 16 weeks after treatment start date will be censored on the day of treatment start date, unless the participant dies within 16 weeks of treatment start date, in which case, death will be an event on date of death.

The censoring and event date options to be considered for the PFS analysis are presented in Table 4.

Table 4. PFS Outcome and Event Dates

Situation	Date of Progression/Censoring	Outcome
No adequate baseline assessment	Date of treatment start date ^a	Censored ^a
PD or death ≤ 16 (or 24) ^b weeks after last adequate tumor assessment or ≤ 16 weeks after treatment start date	Date of PD or death	Event
PD or death > 16 (or 24) ^b weeks after the last adequate tumor assessment ^c	Date of last adequate tumor assessment ^c documenting no PD prior to new anticancer therapy or missed assessments	Censored
No PD		
New anticancer therapy given		

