10.3. Objective Response Status at Each Assessment

Objective response status is determined from the derived target and derived non-target lesion data using the conventions in

Table 11. Derivation of Objective Status Based on Target and Non-Target Lesion Response Assuming No New Lesions*

under the assumption that there are no new lesions identified at the visit.

Objective status after a change in modality that is not considered interchangeable is classified as Not Evaluable (NE).

If there are any new lesions at a time point, then the response is PD at that time point regardless of target or non-target lesion response.

Table 11. Derivation of Objective Status Based on Target and Non-Target Lesion Response Assuming No New Lesions*

Target lesion response	Non-Target lesion response	Objective response status
CR	CR	CR
CR	Non-CR/Non-PD	PR
CR	PD	PD
CR	NAE	PR
PR	CR	PR
PR	Non-CR/Non-PD	PR
PR	PD	PD
PR	NAE	PR
SD	CR	SD
SD	Non-CR/Non-PD	SD
SD	PD	PD
SD	NAE	SD
PD	Any	PD
NAE	PD	PD
NAE	CR	NE
	Non-CR/Non-PD	
	NAE	
NB	CR	CR
	Non-CR/Non-PD	Non-CR/Non-PD
	PD	PD
	NAE	NE
CR	NB	CR
PR		PR
SD		SD
PD		PD
NAE		NE

*If there are any new lesions at a time point, then the response is PD at that time point regardless of target or non-target lesion response.

Abbreviations: CR = Complete Response; PR = Partial Response; SD = Stable Disease; PD = Progressive Disease; NAE = Not All Evaluated; NB = No Baseline; NE = Not Evaluable.

Note: If non-target (or target) lesions are not collected at baseline, then the overall response is equivalent to the target (or non-target) lesions response, respectively.

10.4. Date of Response at Each Assessment/Overall:

The date of CR, PR, PD, non-CR/non-PD, SD, NE is derived as the date of the first radiographic evaluation included in the cluster.

The date of first response for purposes of calculating duration of response and time to response is defined as the first date a CR or PR was documented.

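### The best-overall-response rules have no non-CR/non-PD category, so persistent non-CR/non-PD by IRR is coded Not Evaluable and fails IRR disease control

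*SAP*

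**What the plan says.** **Time-point level.** SAP 7.1.6 lists the responses that make a post-baseline assessment adequate. Beside CR, PR and SD it names "non-CR/non-PD (to be used if only non-measurable disease is present), or PD has been provided by IRR or the investigator". SAP 7.5.5 repeats this for PFS: "An adequate post-baseline assessment is defined as an assessment where a response of CR, PR, SD, non-CR/non-PD, or PD can be determined". In both places SD and non-CR/non-PD are separate entries.

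**BOR level.** SAP 7.5.1 recognises five outcomes. CR and PR need confirmation. The SD rule asks for one read of that status or higher from week 6 on. The PD rule covers early progression, with a 16-week limit, in anyone who has not earned a higher category. Whoever is left falls under the last rule: "NE (Not Evaluable) = all other cases (i.e. not qualifying for confirmed CR or PR and without SD after more than 6 weeks".

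Each NE must then be assigned one of a fixed list of reasons. Under SAP section 10, IRR time-point responses are used as transferred, and only the IRR BOR is derived by program with the appendix rules. Tables 12 and 13 of that appendix have no non-CR/non-PD entry.

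**DCR.** SAP 7.5.4 reads: "DCR is defined as the proportion of participants who have achieved a confirmed CR, confirmed PR or SD", with control required at 168 days or later. The population for all efficacy endpoints is the Safety Set (SAP 7.5), so NE participants stay in the denominator.

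**The concern.** Eligibility requires measurable disease (Protocol 5.1, criterion 7). The efficacy endpoints, however, rest mainly on IRR, which reads the scans separately and does not report back to the investigator (Protocol 7.2.4). IRR may therefore find no target lesion in someone the site enrolled with one. The plan gives that person a valid response at each visit but nowhere to go when the visits are combined.

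Three outputs are at stake: IRR DCR, which is a named secondary endpoint; the NE row of the response table with its reasons; and the swimmer figure, which shows confirmed BOR by IRR. The error in DCR runs one way, downward. If the gap is noticed only at programming, the classification will be chosen with data in hand, in an open-label study that Protocol Version 4 amended to support registration.

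**Working it through.** **1. The plan's own figures.** The only design figures are the exact ORR rules (SAP 4.3). The formula is P(X ≥ r) for X binomial(n, p).

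- Treatment-naïve, n = 60, r = 32: at p = 0.39 this is 0.0170, and at p = 0.65 it is 0.977. With r = 31 the first figure would be 0.0313.
- Previously treated, n = 37, r = 13: at p = 0.20 this is 0.0231, and at p = 0.45 it is 0.916. With r = 12 the first figure would be 0.0517.

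Both stated rules reproduce. NE and non-CR/non-PD are both non-response, so neither rule changes with this point.

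**2. The five BOR rules applied literally.** The visit sequences are illustrative, with no new anticancer therapy.

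| IRR reads | BOR under SAP 7.5.1 |
|---|---|
| non-CR/non-PD every 8 weeks, weeks 8 to 56 | NE |
| non-CR/non-PD at weeks 8, 16, 24; PD at week 32 | NE |
| SD every 8 weeks, weeks 8 to 56 | SD |
| non-CR/non-PD at week 8; CR at weeks 16 and 24 | CR |
| non-CR/non-PD at week 8; one unconfirmed CR at week 16 | SD |
| non-CR/non-PD at week 8; PD at week 16 | PD |

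Only the first two rows go wrong. The first and third rows describe the same course, differing only in whether IRR named a target lesion, yet one is NE and the other SD.

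**3. NE reasons.** If the baseline is adequate, no listed reason describes the first two rows. Scans were done, none was read NE, and no new therapy was started. The reason for progression after week 16 is defined by the absence of any earlier assessment, which is untrue in the second row.

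**4. DCR.** The numerator names CR, PR and SD only, so the first two rows fail although there is no progression at week 24. The loss from k such participants is k/n:

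- Treatment-naïve: 1/60 = 1.7 points.
- Previously treated: 1/37 = 2.7 points.

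The documents give no value for k. Purely to show scale, assume k = 1 to 3:

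- Treatment-naïve: 1.7 to 5.0 points. With an assumed 45/60 controlled, 75.0% (exact 95% CI 62.1 to 85.3) becomes 42/60 = 70.0% (56.8 to 81.2) at k = 3.
- Previously treated: 2.7 to 8.1 points. With an assumed 24/37, 64.9% (47.5 to 79.8) becomes 21/37 = 56.8% (39.5 to 72.9) at k = 3.

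**5. PFS for the same participant.** There are two readings.

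- Baseline adequate, as SAP 7.1.6 implies by providing for "non-CR/non-PD (to be used if only non-measurable disease is present": every scan is adequate, and the participant counts as progression-free in IRR PFS while failing IRR DCR.
- Baseline inadequate, on a strict reading of the measurability wording in SAP 7.1.5: PFS is censored at treatment start (Table 4, and first in the Table 5 hierarchy) unless death comes within 16 weeks. BOR is still NE, now with a reason that fits.

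**The case against.** **The appendix tables are not evidence about IRR.** A reader might take Table 11, whose rows without a baseline target lesion return non-CR/non-PD, and its note ("If non-target (or target) lesions are not collected at baseline, then the overall response is equivalent to the target (or non-target) lesions response, respectively") as proof that the SAP expects IRR to find no target lesion. Section 10 does not support that: those rules derive investigator time points, where a missing target lesion is to be reported as a protocol deviation. This objection stands. For IRR the case rests on SAP 7.1.6, which names IRR expressly, and on 7.5.5. How IRR handles such a baseline belongs to its charter, which is not among the documents.

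**Another source may fill the gap.** SAP 10.4.1 refers to an Oncology Rulebook for BOR and presents Tables 12 and 13 as specific cases and examples. The Rulebook is not available here and may hold the missing category. That limits certainty about what will be programmed. It does not rescue the text, because 7.5.1 already sends every other case to NE. If the two differ, they need reconciling.

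**The PFS contradiction is not certain.** A reader might infer that IRR DCR and IRR PFS must conflict. They do so only if the baseline is adequate. SAP 7.1.5 and 7.1.6 pull in different directions, so the conflict is conditional.

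**Counting non-CR/non-PD widens the protocol's DCR.** The protocol names CR, PR and SD only. However, Protocol 8.4.2.2 leaves further DCR detail to the SAP, so the SAP can settle this openly.

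**The consequence is small.** DCR is secondary, has a confidence interval but no test, and individual IRR responses are listed. This is fair, and it limits the priority rather than the correctness of the point.

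**Conclusion.** Wrong as written, for a secondary endpoint and at low expected frequency. Followed literally, SAP 7.5.1 and 7.5.4 turn an evaluable, non-progressing participant into NE and a DCR failure.

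Two stronger conclusions are tempting and not supported. First, not every participant without an IRR target lesion becomes NE: a confirmed CR stays CR, an unconfirmed CR at 6 weeks or later gives SD, and progression by week 16 gives PD. Second, no bias of a given number of points can be claimed for the trial. The documents give no rate of IRR baselines without a target lesion. Any assumed rate is also an upper bound on the effect, since only those still controlled at 24 weeks or later change DCR.

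What can be stated is 1.7 or 2.7 points per such participant. This assumes cohorts of 60 and 37, IRR reporting as SAP 7.1.6 allows, and no contrary rule in the unseen Rulebook or charter. Primary ORR is unaffected.

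**What to change.** In the SAP:

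- **7.5.1, new category:** *Non-CR/non-PD = at least one non-CR/non-PD assessment ≥6 weeks after start of treatment in a participant with no target lesion at baseline per that assessor (and not qualifying for CR or SD).* Remove these cases from NE.
- **7.5.1, PD rule:** add non-CR/non-PD to its exclusions, so that the order of precedence matches SD. Otherwise non-CR/non-PD at week 8 followed by PD at week 16 stays PD, while Table 12 gives SD to a PR followed by PD once the minimum SD duration is met.
- **Table 12:** add the matching rows.
- **7.1.5:** state that a baseline with only non-target lesions is adequate for this purpose, which removes the conflict with 7.1.6.
- **7.5.4:** count non-CR/non-PD with SD under the existing 168-day condition, for IRR and investigator alike, and show its number separately.

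Check the wording against the Oncology Rulebook and the IRR charter at the same time. The cost is a few lines of text and one programming branch, with no new data. It should be done before the final analysis so that the classification is not chosen after seeing results.

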7.2.3. Tumor Imaging During Treatment

The first imaging assessment should be performed as follows:

- 8 weeks after the first dose of study treatment
- Every 8 weeks (56 days ± 7 days) for 12 months, and then every 12 weeks (± 7 days) thereafter until disease progression is determined or until any of the criteria in Section 7.1.4.2 are met.
- Imaging assessments may be performed more frequently if clinically indicated.

Imaging should follow calendar days and should not be delayed, irrespective of study treatment administration (i.e. delays in cycles or dose holds).

Per RECIST v1.1, responses (PR or CR) should be confirmed by a repeat radiographic assessment. The scan for confirmation of response may be performed no sooner than 4 weeks after the first documented response and no later than the next per-protocol scheduled scan, whichever is clinically indicated.

Radiographic disease assessments should be performed until disease progression per RECIST v1.1, withdrawal of consent, initiation of subsequent anticancer therapy, patient is lost to follow-up, death or defined end of study (see Section 4.5 and Section 6.8).

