8.2. Sample Size Determination

The sample size calculation is based on the primary endpoint of ORR as determined by IRR per RECIST v1.1. The hypotheses to be tested are described in Section 8.1. With 60 evaluable treatment-naïve patients with $BRAF^{V600E}$ NSCLC, the power is greater than 95% to test the null hypothesis that the ORR is less than or equal to 39% versus the alternative hypothesis that it is greater than 39% assuming an alternative target rate of 65% with a one-sided $\alpha \le 0.025$ based on a single-stage design using exact test. The null hypothesis will be rejected if ≥ 32 confirmed objective responses are observed. With 37 evaluable previously treated patients with $BRAF^{V600E}$ NSCLC, there is at least 90% power to test the null hypothesis that the ORR is less than or equal to 20% versus the alternative hypothesis that it is greater than 20% assuming an alternative target rate of 45% with a one-sided $\alpha \le 0.025$ based on a single stage design using exact test. The null hypothesis that it is greater than 20% assuming an alternative target rate of 45% with a one-sided $\alpha \le 0.025$ based on a single stage design using exact test. The null hypothesis that it is greater than 20% assuming an alternative target rate of 45% with a one-sided $\alpha \le 0.025$ based on a single stage design using exact test. The null hypothesis will be rejected if ≥ 13 confirmed objective responses are observed.
At least 60 treatment-naïve and 37 previously treated $BRAF^{V600E}$ NSCLC patients will be enrolled and treated. It is not expected that more than 107 patients with any $BRAF^{V600}$ mutation will be enrolled and treated.

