5.2. Safety Analysis Set

The SS includes all participants who receive at least 1 dose of study treatment.

Unless otherwise specified, the safety analysis set will be the default analysis set used for all efficacy and safety analyses.

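### The optional COVID-19 sensitivity analysis of ORR excludes for any missed scan at any time, so it can drop confirmed responders and make a sound primary result look fragile

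*SAP*

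**What the plan says.** SAP 7.5.1 states that the effect of assessments missing because of COVID-19 will be evaluated and that, where this shows a need, ORR by IRR may be recalculated as a sensitivity analysis, "excluding participants with tumor assessments missing due to COVID19 from SS". It gives no trigger, no minimum number of missed scans, no time limit, and no exception for a participant whose response is already confirmed.

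Four other provisions matter here:

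- SAP 5.2 makes the Safety Set (SS) the basis of the primary ORR: "the safety analysis set will be the default analysis set used for all efficacy and safety analyses".
- Protocol 7.2.3 schedules scans "Every 8 weeks (56 days ± 7 days) for 12 months, and then every 12 weeks (± 7 days) thereafter until disease progression is determined".
- SAP 7.5.1 defines confirmation with a minimum gap and no maximum: "PR = at least 2 determinations of PR or better at least 4 weeks apart before progression". Table 13 of SAP Appendix 1 includes a sequence in which a time point that was not assessed lies between two complete responses and CR is still awarded.
- SAP 7.5 sets the final treatment-naïve ORR analysis late: it "will take place after 14 months from the enrollment of the last treatment-naïve participant".

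**The concern.** Read literally, the rule removes a participant with PR at weeks 8 and 16 who misses week 40 because of COVID-19, although that scan cannot alter the best overall response. The chance of ever missing a scan grows with the number of scans scheduled, and that number depends on time to progression. Exclusion is therefore tied to the outcome being estimated. Long responders are the most exposed, and participants who progress early the least.

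The analysis is meant to show whether missed scans disturbed the primary result. With outcome-linked exclusion it can show a drop in ORR when no response was lost, and the natural reading would be that the primary estimate is fragile. Nor does it answer the useful question. The SS already counts a response lost to a missed scan as a non-response, so what is unknown is how much higher ORR might have been.

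**Working it through.** **1. The plan's own design.** Exact binomial tails for the rules in SAP 4.3:
- 32 or more of 60: one-sided alpha 0.0170 at 39%, power 0.977 at 65% (31 or more would give alpha 0.0313).
- 13 or more of 37: alpha 0.0231 at 20%, power 0.916 at 45%.

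Both reproduce. They belong to the primary SS analysis, and nothing below changes them.

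**2. Scan counts.** The schedule gives weeks 8, 16, 24, 32, 40, 48, 60, 72 and so on. Protocol 2.1.2 cites median DOR of 10.4 months (treatment-naïve) and 9.0 months (previously treated) for the comparator regimen. At 30.4375 days per month these are 45.2 and 39.1 weeks. With first response at week 8, progression falls near week 53 (seen at week 60, the 7th scan) or week 47 (seen at week 48, the 6th scan). A non-responder progressing by week 24 has 3 scans.

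**3. Closed form.** Let m be the chance that a scheduled scan is missed because of COVID-19, kR and kN the scans for responders and non-responders, and p the true ORR. Then

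ORR after exclusion = p(1−m)^kR / [p(1−m)^kR + (1−p)(1−m)^kN].

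Example with m = 5%, kR = 7, kN = 3, p = 65%: 0.65 × 0.698 = 0.454 and 0.35 × 0.857 = 0.300, so ORR = 0.454/0.754 = 60.2%. Responders are excluded at 30%, non-responders at 14%.

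| p | Scans (kR, kN) | m = 2% | m = 5% | m = 10% |
|---|---|---|---|---|
| 65% | 7, 3 | 63.1% | 60.2% | 54.9% |
| 65% | 6, 4 | 64.1% | 62.6% | 60.1% |
| 65% | 5, 5 | 65.0% | 65.0% | 65.0% |
| 45% | 7, 3 | 43.0% | 40.0% | 34.9% |

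With equal scan counts the shift vanishes, so the bias comes from the difference in exposure.

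**4. Simulation on the protocol schedule** (200,000 participants per scenario, two responses required before progression). Assumptions not in the documents: first response at week 8 (70%) or week 16 (30%), median non-responder PFS 5.5 months, follow-up 14 to 30 months, equal chance of a miss at every scan. The median DORs are those in step 2. In the treatment-naïve setting mean scheduled scans were 7.1 for responders and 3.7 for non-responders.

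| Setting | Analysis | m = 2% | m = 5% | m = 10% |
|---|---|---|---|---|
| Treatment-naïve | Full SS | 66.1% | 65.3% | 64.8% |
| Treatment-naïve | After exclusion | 64.8% | 62.1% | 57.8% |
| Treatment-naïve | Fall (points) | 1.3 | 3.2 | 7.0 |
| Previously treated | Full SS | 47.4% | 47.0% | 46.2% |
| Previously treated | After exclusion | 46.1% | 43.8% | 39.8% |
| Previously treated | Fall (points) | 1.3 | 3.2 | 6.4 |

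Varying treatment-naïve non-responder PFS from 3 to 8 months moves the result after exclusion at m = 10% between 55.6% and 59.5%.

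**5. Timing of misses.** If misses occur only in the first three scans, SS and exclusion agree (65.4% and 65.5% at m = 5%). A six-month outage early in an assumed 24-month accrual gives 0 to +1.2 points. A mid-accrual or late outage gives −1 to −10 points.

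**6. What a reader would see.** Suppose 39/60 respond: 65.0%, Clopper-Pearson 95% CI 51.6 to 76.9%.
- At m = 5% the simulated exclusion rates (29.3% and 18.7%) leave 39 × 0.707 = 27.6 responders and 21 × 0.813 = 17.1 non-responders, about 28/45: CI 46.5 to 76.2%.
- At m = 10% (50.2% and 33.2%) they leave 19.4 and 14.0, about 19/33: 57.6%, CI 39.2 to 74.5%. The lower limit now sits at the 39% null, partly from the shift and partly from the smaller sample.

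**The case against.** The analysis is conditional: the impact is evaluated first, and the recalculation follows only if needed. A late miss after a confirmed response gives no reason to run it. Only COVID-19 misses count, and Protocol 18.7 allows imaging at another facility, which should keep them few. Participants with stable disease are also non-responders and go on being scanned, which narrows the gap in scan counts. There is an offsetting effect as well: an early miss can leave a true responder unconfirmed, and exclusion removes that loss (0.3 to 1.7 points in the treatment-naïve simulation). All of this stands and limits the size of the point. It does not repair the rule, because once the analysis is run for any reason the late misses trigger exclusion too.

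A reader might infer more than the documents support:

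- That the primary ORR or the 32/60 and 13/37 thresholds are compromised. They are not. They apply to the SS, and no success criterion is attached to the sensitivity analysis. A downward shift cannot create a false efficacy claim.
- That the answer must be wrong. Direction and size depend on when misses occur, which the documents do not say.
- That affected participants disappear from view. They stay in the primary analysis, SAP 7.3 gives COVID-19 deviations a separate table and listing, and SAP 7.5.1 lists responses by participant and date.
- That the fall is much larger. Assuming 8 and 3 scans gives 62.7%, 59.0% and 52.3% from 65%, falls of 2.3, 6.0 and 12.7 points, about 1.8 times the simulated ones. Eight scans means staying on schedule to week 72, beyond what the cited median DORs imply.

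**Conclusion.** The concern holds as a minor defect in an optional analysis. The exclusion has no time window and ignores whether the missed scan could matter, so under roughly even or late missingness it removes confirmed responders disproportionately and understates ORR. With assumed per-scan missing rates of 2%, 5% and 10%, the fall is about 1, 3 and 7 points from about 65%. With early misses it is about zero or slightly upward. The missing rates, non-responder PFS, response timing and accrual pattern are assumptions; the scan schedule, the confirmation rule and the reference DORs come from the documents. The consequence is a possible false signal that the primary result is not robust. The primary result itself is unaffected.

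**What to change.** Replace the exclusion in SAP 7.5.1 with bounds in the full Safety Set:

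- Lower bound: the primary analysis as it stands.
- Upper bound: count as responders all participants with neither a confirmed response nor documented PD before the scan missed because of COVID-19. This includes those with SD, with an unconfirmed CR or PR, or with no evaluable scan. SD must be included because SD, then a missed scan, then PD could hide a response.
- All other participants keep their outcome.

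Alternatively, keep an exclusion but limit it to COVID-19 misses in a fixed early window, for example the first three scheduled scans (weeks 8, 16 and 24), applied regardless of outcome. In the treatment-naïve simulation this gave 66.1%, 65.5% and 64.8% at 2%, 5% and 10% missed, within 0.2 points of the full SS. A small gap can remain when non-responders progress quickly: 45.2% against 46.3% in the previously treated setting at 10% missed, with a 3-month median non-responder PFS.

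The cost is a sentence or two in the SAP and a little programming, with no new data. The upper bound is deliberately extreme and should be labelled as a bound, not an estimate.
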